#### **Data Collection procedure:**

#### **Analysis method:**

Free hand (countersink guided) and surgical guide surgeries were carried out by a parallel surgical kit (Dentsply®, MIS, M4, Germany), following the manufacturer's recommendations. The surgical guide surgeries were carried out using a dedicated (Dentsply®, MIS, M4 Germany) following the above-mentioned surgical plan. Both of the implants were performed for the same patient, on the same day and with the same devices. One implant per side was placed free hand, countersink guided and the other side with a computer-assisted implant guide.

With Blue Sky Plan 4 (Blue Sky Bio, Grayslake, IL, USA) software, the post-operative fixture was extracted as an STL file by segmentation the DICOM file of the CBCT taken after surgery used 3D slicer program as show in Figure 1.

Figure 1: show segmentation the DICOM file of the CBCT taken after surgery used 3D slicer program.

Then, the STL file post-operative fixture imported to Blue Sky Plan 4 program and superimposing with planned fixture on the CBCT on the planned implant location before surgery as presented in Figure 2.

Figure 2: show import the DICOM file post-operative fixture to Blue Sky Plan 4 program and superimposing with the CBCT which have the planned implant location before surgery.

More than twenty points marked on the two images using a point-based automatic image registration algorithm to ensure correspondence as show in Figure 3.

Figure 3 : aligned using a point-based automatic image registration algorithm.

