#### Measure the deviation for each parameter:

The definitions concerning accuracy outcome measures are as follows: The primary outcome was angular deviation defined as the angle closed by the principal axis of the planned implant and the principal axis of the inserted implant in degrees. The secondary outcomes were crestal global deviation; the distance between the center of the coronal end of the planned and the inserted implants in millimeters, apical global deviation; the distance between the apical endpoints of the planned and the inserted implants in millimeters, and vertical linear deviation ; the distance between perpendicular line on the hexagon of planned implant and another line draw parallel to it on the hexagon of actual implant in millimeters, lateral linear deviation; the distance between vertical line on the long axis of planned implant and another line draw parallel to it on the long axis of actual implant in millimeters, apical vertical deviation ; the distance between perpendicular line on the apex of planned implant and another line draw parallel to it on the apex of actual implant in millimeters, apical lateral deviation ; the distance between vertical line on the long axis of planned implant and another line draw parallel to it on the long axis of actual implant in millimeters, Two anatomical parameters were added to these ones : the distance from the inferior alveolar nerve (IAN) and the distance from the maxillary sinus (MS).

Primary outcome is Angular deviation of the final position to the planned implant position. Meanwhile, secondary outcomes are described by the following eight measurements.

Figure 4: Deviation parameters between the planned implant position (blue) and placed implant position (yellow): (a) Lateral Linear deviation (mm); (b) Vertical Linear deviation (mm); (c) Global Crestal deviation (mm); (d) Apical Lateral deviation (mm); (e) Apical Vertical deviation (mm); (f) Apical Global deviation (mm); a, Angular deviation (degree). (Ngamprasertkit et al., 2022)

The real measurements of the primary and secondary outcomes using Blue Sky Plan 4 Software are presented in Figure 5.

linear deviation (mm); (e) lateral linear deviation (mm); (f) crestal global deviation (mm); (g) apical vertical deviation (mm); (h) apical global deviation.

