#### **Data Analysis**

The researcher employed the Statistical Package for the Social Sciences (SPSS) version 22 program for both data entry and statistical analysis. The data analysis process comprised two stages: first, descriptive analysis to summarize the data, followed by an inferential analysis that elucidated the relationships between the variables under investigation. Also, the Central tendency measures were performed to describe the collected data from patients. Exact Fisher's Test, Chi-square Test and Independent t-Test were used to examine the possible relationship between variables. The confidence interval was considered at 95% and a margin of error 5%. P-value less than 0.05 was considered to indicate a statistically significant difference.

Categorical outcomes were presented as absolute and relative frequencies. A bivariate analysis using Independent t-Test, or Fisher's exact test when application conditions were not achieved, was used to compare the groups. Differences between groups of scale variables were explored using parametric (Student's t test for independent or paired samples) or nonparametric tests. Chi square test was used to test the relationship between two categorical. In the present study the Independent t-Test, Fisher's exact test and Chi square test as well as median were used where the data was classified nonparametric.

Abbreviations:

Symbol	Description
СВСТ	Cone Beam Computed Tomography
CAD	Computer Aided Design
CAM	Computer-aided manufacturing
CAI	Computer Assisted Inspection
DICOM	Digital Imaging and Communications in Medicine
GIS	Guided Implant Surgery
STL	Standard Tessellation Language OR Standard Triangulated
AD	Angular deviation
CGD	crestal global deviation
VLD	Vertical Linear Deviation
LLD	Lateral Linear Deviation
AGD	apical global deviation
ALD	Apical Lateral Deviation
MS	Maxillary Sinus
IAN	Inferior Alveolar Nerve
s-CAIS	Static computer-assisted implant surgery
IOS	Intra oral scan
3D	Three-dimensional
FG	Fully guided
FH	Freehand
CS	Countersink
SD	Standard deviation
AVD	apical vertical deviation
FHM	free hand method
SGM	surgical guide method
FH	free hand

SG	surgical guide
PG	pilot guide
FG	fully guided

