## **Declaration Funding:**

I declare that this article has been composed solely by myself and that it has not been submitted, in whole or in part, in any previous application for a degree. Except where states otherwise by reference or acknowledgment, the work presented is entirely my own.

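### No masking to technique is described for segmentation, registration or measurement, and manual steps are not identified, so technique-specific reading bias cannot be excluded

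*Combined protocol and SAP*

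**What the plan says.** The Analysis method section sets out the measurement chain.

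- **Segmentation.** In the plan's words, "the post-operative fixture was extracted as an STL file by segmentation the DICOM file of the CBCT taken after surgery". No threshold, operator or masking is given.
- **Registration.** "More than twenty points marked on the two images using a point-based automatic image registration algorithm". The Figure 3 caption describes the images as "aligned using a point-based automatic image registration algorithm".
- **Layout.** Each patient received both techniques on the same day, one on each side.

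The section headed Measure the deviation for each parameter defines the outcomes.

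- **Primary outcome, angular deviation:** "the angle closed by the principal axis of the planned implant and the principal axis of the inserted implant in degrees".
- **CGD and AGD:** distances between corresponding end points of the planned and placed implants.
- **VLD, LLD, AVD and ALD:** distances between drawn lines. For VLD, for example, the second line is "another line draw parallel to it on the hexagon of actual implant in millimeters".
- **Anatomical outcomes:** distances to the inferior alveolar nerve (IAN) and the maxillary sinus.

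On software the plan says only: "The real measurements of the primary and secondary outcomes using Blue Sky Plan 4 Software are presented in Figure 5". The Study design section mentions control of bias in general terms and names no procedure. The text does not state the number of readers, their independence from the surgeon, any masking, or any repeat reading.

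**The concern.** The surgeon cannot be masked to technique, but the person measuring the scans can. As the plan is written, nothing prevents the reader from knowing which implant was guided while segmenting it, placing lines on it or locating its axis.

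Any discretion exercised differently on the two sides adds directly to the estimated difference between techniques. Within-patient pairing removes what the two sides share, such as the patient and the scanner. It does not remove an error that follows the technique. With 15 patients, a modest shift of this kind could produce a significant result where no difference exists, or could enlarge or hide a real one.

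**Working it through.** **Step 1. Where could a reader's judgement enter?**

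| Step or outcome | What the plan states | What it leaves open |
|---|---|---|
| Segmentation of the placed implant | Done from the post-operative scan | Operator, threshold, masking |
| Registration | More than twenty points; algorithm called automatic | Who or what marks the points; one registration per patient or per implant |
| Angular deviation (primary) | Angle between two implant axes | How the placed implant's axis is located |
| CGD, AGD | Distance between end points | How the end points are located |
| VLD, LLD, AVD, ALD | Distance between drawn lines | Who draws them, and with what knowledge of technique |
| IAN and sinus distances | Named only | How they are read |

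Drawn lines reach only the four linear secondary outcomes. The primary angle is exposed by another route: the placed implant's axis comes from the segmented fixture, and its position relative to the plan comes from the registration. Neither step is stated to be free of a reader's choices.

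**Step 2. Could an error be specific to technique?** If one scan and one registration serve both implants in a patient, registration error acts on both sides and is hard to steer toward one technique. The plan does not say that this was done. Segmentation and measurement of each implant are the more plausible routes.

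**Step 3. How much would a shift matter?** The documents give no SD, effect size, power figure or reading error, so there is no stated figure to reproduce. What follows is an illustration.

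Inputs:
- From the abstract: 30 implants in 15 patients, hence n = 15 pairs.
- From Data Analysis: significance at P < 0.05. Sidedness is not stated; two-sided is assumed.
- Assumed: SD of paired angular differences s = 2, 3 or 4 degrees.
- Assumed: technique-specific shift b = 0.5 or 1 degree, with no true difference.

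For a paired t-test the noncentrality is δ = b√n / s, with 14 degrees of freedom and critical value 2.145. The false-positive rate is P(|T| > 2.145), where T is noncentral t with parameter δ.

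| Shift b | s = 2 | s = 3 | s = 4 |
|---|---|---|---|
| 0 | 5% | 5% | 5% |
| 0.5 degree | δ = 0.968, 14.7% | δ = 0.645, 9.2% | δ = 0.484, 7.4% |
| 1 degree | δ = 1.936, 43.8% | δ = 1.291, 22.5% | δ = 0.968, 14.7% |

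Example: 0.5 × √15 / 3 = 0.645.

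**Step 4. Does the test chosen change this?** Data Analysis mainly names the independent t-test. If the two sides are uncorrelated and s = 3, δ is unchanged and the degrees of freedom become 28. The rates are then 9.6% for a 0.5 degree shift and 23.9% for 1 degree. The choice of test gives no protection.

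**The case against.** Several stronger readings are tempting, and the documents do not support them.

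- **That the registration points were placed by hand.** The plan and the Figure 3 caption both call the algorithm automatic, and the statement that points were marked leaves the operator open. The figures, which might show what is manual, were not available to me.
- **That the primary outcome is itself a subjective, hand-drawn measure.** It is defined as an angle between axes, and the software may locate those axes without a reader. The plan does not say. Only the four linear deviations are defined by drawn lines.
- **That one unmasked person measured everything.** Data Analysis says "The researcher employed the Statistical Package for the Social Sciences (SPSS) version 22 program for both data entry and statistical analysis", which concerns data entry and statistics, not the reading of scans. The sentence "Except where states otherwise by reference or acknowledgment, the work presented is entirely my own" belongs to an authorship declaration and is not a statement about who measured.
- **That readings were shifted toward the guide.** Nothing shows a shift or its direction. Free supply covered both the guides and the implants, and implants were used on both sides. It is a reason to protect the assessment, not evidence of bias.
- **That assessment was unmasked.** Silence supports only the statement that masking is not described.

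It is also fair to say that the assumed shifts have no source in the documents, and that coding cannot fully mask a reader who sees the anatomy.

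All of this narrows the point without removing it. The chain includes segmentation and drawn lines, technique can be identified from the side, and no safeguard is described.

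**Conclusion.** The point holds in a limited form. The plan does not identify its manual steps and describes no masking at any of them, so technique-specific reading bias cannot be excluded. The exposure is direct for VLD, LLD, AVD and ALD, and indirect, through the fixture axis and the registration, for angular deviation.

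The calculated rates show only that a shift of 0.5 to 1 degree would matter with 15 pairs if it existed. They rest on assumed SDs, assumed shifts, a two-sided test and no true difference. They do not estimate bias in this trial. The change should be made because it is cheap and uses existing files and staff. If assessment was in fact masked or fully automated, a sentence saying so and describing how would settle the matter.

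**What to change.** 1. State which steps are manual and which are automatic, and who carries out each.
2. Use one segmentation setting and one registration per patient, both locked before any implant is measured.
3. Export each planned and placed fixture pair under a random code with patient and side removed. An existing team member who does not measure holds the key.
4. Compute the angle, CGD, AGD and, where possible, the four linear deviations from axis and end-point coordinates.
5. Read the IAN and sinus distances, which need the anatomy, from coded views without technique labels.
6. Lock all 30 sets of values before linking them to technique.

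If measurement is already complete, re-measure the stored files under code, or report the assessment as unmasked.

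The cost is some clerical time for coding 30 fixture pairs and keeping the key. No new scans, patients or additional reader are needed. Masking may remain imperfect wherever anatomy is visible, and the report should say so.

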#### Measure the deviation for each parameter:

The definitions concerning accuracy outcome measures are as follows: The primary outcome was angular deviation defined as the angle closed by the principal axis of the planned implant and the principal axis of the inserted implant in degrees. The secondary outcomes were crestal global deviation; the distance between the center of the coronal end of the planned and the inserted implants in millimeters, apical global deviation; the distance between the apical endpoints of the planned and the inserted implants in millimeters, and vertical linear deviation ; the distance between perpendicular line on the hexagon of planned implant and another line draw parallel to it on the hexagon of actual implant in millimeters, lateral linear deviation; the distance between vertical line on the long axis of planned implant and another line draw parallel to it on the long axis of actual implant in millimeters, apical vertical deviation ; the distance between perpendicular line on the apex of planned implant and another line draw parallel to it on the apex of actual implant in millimeters, apical lateral deviation ; the distance between vertical line on the long axis of planned implant and another line draw parallel to it on the long axis of actual implant in millimeters, Two anatomical parameters were added to these ones : the distance from the inferior alveolar nerve (IAN) and the distance from the maxillary sinus (MS).

Primary outcome is Angular deviation of the final position to the planned implant position. Meanwhile, secondary outcomes are described by the following eight measurements.

Figure 4: Deviation parameters between the planned implant position (blue) and placed implant position (yellow): (a) Lateral Linear deviation (mm); (b) Vertical Linear deviation (mm); (c) Global Crestal deviation (mm); (d) Apical Lateral deviation (mm); (e) Apical Vertical deviation (mm); (f) Apical Global deviation (mm); a, Angular deviation (degree). (Ngamprasertkit et al., 2022)

The real measurements of the primary and secondary outcomes using Blue Sky Plan 4 Software are presented in Figure 5.

linear deviation (mm); (e) lateral linear deviation (mm); (f) crestal global deviation (mm); (g) apical vertical deviation (mm); (h) apical global deviation.

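### Lateral linear and apical lateral deviation share one drawn-line definition with no view or level named; both should be computed from the registered 3D fixtures

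*Combined protocol and SAP*

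**What the plan says.** All from the combined protocol and SAP.

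The section *Measure the deviation for each parameter* uses two kinds of definition.

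- **Point to point.** Crestal global deviation (CGD) is "the distance between the center of the coronal end of the planned and the inserted implants in millimeters". Apical global deviation (AGD) is the same kind of distance between the apical end-points.
- **Drawn parallel lines.** LLD is "lateral linear deviation; the distance between vertical line on the long axis of planned implant and another line draw parallel to it", the second line lying on the long axis of the placed implant. ALD is "apical lateral deviation ; the distance between vertical line on the long axis of planned implant and another line draw parallel to it", and its definition ends in the same way. Vertical linear deviation (VLD) is "the distance between perpendicular line on the hexagon of planned implant and another line draw parallel to it on the hexagon of actual implant". Apical vertical deviation (AVD) is "the distance between perpendicular line on the apex of planned implant and another line draw parallel to it on the apex of actual implant".

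No view, slice, plane or combination of views is given for the four line-based outcomes, and no level along the implant is given for LLD or ALD. The readings come from the planning software: "The real measurements of the primary and secondary outcomes using Blue Sky Plan 4 Software are presented in Figure 5".

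Under *Analysis method*, the placed fixture is segmented from the post-operative CBCT as an STL object. The plan then describes "the STL file post-operative fixture imported to Blue Sky Plan 4 program and superimposing with planned fixture", with registration on more than twenty points. Both fixtures therefore lie in one 3D frame. No calculation from coordinates is described for the lateral or vertical components.

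**The concern.** There are three linked problems, and they bear mainly on LLD and ALD.

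1. **Identical definitions.** Two separately listed secondary outcomes have the same operational wording. Someone following the text has no instruction that would produce two different numbers.
2. **No level.** When angular deviation is above zero, a line parallel to the planned axis cannot also run along the placed axis. The measurer must choose a point on the placed implant to draw it through, and the gap changes with that choice.
3. **No view.** A gap between two lines drawn in one view is a projection. Lateral displacement towards or away from the viewer does not appear in it.

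At stake is the meaning of two of the eight secondary outcomes. They could be understated and noisier than the images allow, and could fail to agree with CGD and AGD measured on the same implants.

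**Working it through.** The plan states no value, SD or expected size for any of these deviations, so there is no figure to reproduce. The check is geometric. All millimetre values, angles and spreads below are assumptions.

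**Set-up.** Let **u** be the unit vector of the planned axis and **d** the vector from the planned to the placed coronal centre. Then:

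- vertical = |**d**·**u**|
- lateral = |**d** − (**d**·**u**)**u**|
- global = |**d**|, and global² = vertical² + lateral²

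**Lateral reading in one view.** If the view contains **u** and lies at angle φ to the lateral displacement, the reading is lateral × |cos φ|.

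| φ | Share of true lateral deviation read |
|---|---|
| 0° | 100% |
| 30° | 87% |
| 45° | 71% |
| 60° | 50% |
| 90° | 0% |

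If the error direction is random relative to the view, the mean share is 2/π = 0.637. The share is below one half when φ lies between 60° and 90°, which is 30/90 = one implant in three.

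If the spread of the error differs in and out of the view (normal components, simulated), the mean share per implant is:

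| Out-of-view SD ÷ in-view SD | Mean share |
|---|---|
| 1/3 | 83% |
| 1/2 | 77% |
| 1 | 64% |
| 2 | 48% |
| 3 | 40% |

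**Added noise.** With random direction, the coefficient of variation (CV) of the reading is √[((1 + CV²)/2)/(2/π)² − 1]. For a true CV of 0.5 this is √(0.625/0.405 − 1) = 0.74. True CVs of 0.3 and 0.7 become 0.59 and 0.92.

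**Vertical reading.** Take lateral 1.0 mm at 30° and vertical 0.5 mm, so that global = √(1.00 + 0.25) = 1.12 mm. Views at 0°, 45°, 90° and 120° that contain the planned axis read lateral as 0.87, 0.97, 0.50 and 0.00 mm, but vertical as 0.50 mm every time. The vertical outcomes change only if the view is tilted off the planned axis. With tilt t and 1.0 mm of lateral error out of the view, the reading is 0.5 cos t ∓ 1.0 sin t:

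- 5°: 0.41 or 0.59 mm
- 10°: 0.32 or 0.67 mm
- 20°: 0.13 or 0.81 mm

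The error can go either way.

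**Agreement with the global deviation.** In the same example, the 90° view gives √(0.50² + 0.50²) = 0.71 mm from the components, against a point-to-point global deviation of 1.12 mm.

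**Level.** Over an assumed 10 mm of implant length, the lateral gap changes by up to 10 × sin(angular deviation): 0.35 mm at 2°, 0.70 mm at 4° and 1.05 mm at 6°.

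**The case against.** The strongest reply is that a single on-screen view is an inference. The text speaks of lines drawn on the two implants and never of a view or slice. Figures 4 and 5, which show the construction, could not be seen. If the lines were placed in 3D, no displacement is lost. This stands: the text establishes that the view is unspecified, not that projection loss occurred.

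It can also be said that the name of ALD, and its separate letter in the caption of Figure 4, point to the apex. That is a fair guess at the intention, but the definition does not say so.

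A reader might infer three stronger conclusions. The documents do not support them.

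- **That all four line-based outcomes are understated.** A view containing the planned axis captures the whole axial displacement, so VLD and AVD lose nothing in it. A tilted view can raise or lower them, so there is no systematic understatement.
- **That the comparison of techniques is biased.** The two implants of a patient are on opposite sides, but the same anatomical view on each side can lose the same component. With random error direction both techniques shrink by the same expected factor, and the ratio of their means is unchanged. Unequal loss would need a further assumption that nothing in the plan supplies.
- **That a 3D calculation is exact.** Segmentation and registration error remain, and the plan reports neither.

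**Conclusion.** The point holds for LLD and ALD. It is certain from the text that they share one definition, that no level is named and that no view is named. It is certain from geometry that the gap depends on the level once the axes diverge, and that a single-view lateral reading can equal or understate the true value but never exceed it.

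The size is conditional on a single view having been used: a mean capture of 64% under random direction, with a range of about 40% to 83% over the spread ratios examined. VLD and AVD are at risk only from an off-axis view.

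Only secondary outcomes are touched, so the change is one the plan should make rather than one on which the primary result depends. It goes beyond asking for more detail, because the registered fixtures already permit a better-defined measurement.

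**What to change.** Replace the four drawn-line definitions with values computed from the registered fixtures:

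- With **u** the unit vector of the planned axis and **d** the vector from the planned to the placed coronal centre, set VLD = |**d**·**u**| and LLD = |**d** − (**d**·**u**)**u**|. VLD is an absolute value, so that opposite signs do not cancel in a group mean. LLD is the length of the vector that remains after removing the axial part, not a difference of two lengths.
- Compute AVD and ALD in the same way from the planned and placed apical end-points.
- Compare CGD and AGD, as read separately in the software, with √(VLD² + LLD²) and √(AVD² + ALD²). Set a tolerance in advance and re-measure any implant outside it. The check is informative only if the global deviations are measured separately; computed from the same coordinates, they agree by construction.
- State that segmentation and registration error remain in all these values.

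This removes any projection loss and separates LLD from ALD. If the existing readings were already made in 3D at the right levels, the new values should agree with them within measurement error.

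**Cost:** four end-points (planned and placed, coronal and apical) for each of 30 implants, 4 × 30 = 120 points, and a spreadsheet formula. No new scans or patients are needed. This assumes that the software can export the coordinates.

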## Materials and methods:

A total of 30 implants of the same brand and type (M4 MIS Dentsply, Germany) were placed in15 partially edentulous volunteers in need of implantation in the mandible or maxilla or both. All cases were digitally planned using data from cone beam computed tomography, and the comparison of the planned and actual implant positions was performed using a medical image analysis software (blue sky plan 4). Post-op. CBCT was used for nine measurements representing the deviations in angles, implant shoulders and apexes. The outcome parameter was angular deviation (AD, degrees), crestal global deviation (CGD, mm), vertical linear deviation (VLD, mm), lateral linear deviation (LLD, mm), apical global deviation (AGD, mm), apical vertical deviation (AVD, mm), apical lateral deviation (ALD, mm), distance from maxillary sinus and distance from inferior alveolar nerve. Statistical analysis was performed using Fisher's exact test to compare the proportion between groups and Chi square test to test the relationship between two categorical variables.

Keywords: Countersink guided, Quasi experimental study, fully guided, Accuracy, partially edentulous.

**Trial registration:** Palestinian Health Research Council ethical approval attains from the Helsinki committee trial registration number (PHRC/HC/1242/23) at date of registration in it's meeting on 23/02/2023.

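### Do the identical written definitions of lateral linear deviation and apical lateral deviation leave two secondary outcomes undefined?

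*Combined protocol and SAP*

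**What the plan says.** The section headed Measure the deviation for each parameter defines every accuracy outcome in one long sentence. The two lateral outcomes read:

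- Lateral linear deviation (LLD): "lateral linear deviation; the distance between vertical line on the long axis of planned implant and another line draw parallel to it".
- Apical lateral deviation (ALD): "apical lateral deviation ; the distance between vertical line on the long axis of planned implant and another line draw parallel to it".

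Both then end with the same clause, which puts the second line on the long axis of the implant as placed. Neither says at what height the distance is read.

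The other two crestal and apical pairs in that sentence do name a level:

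- Crestal global deviation (CGD) is "the distance between the center of the coronal end of the planned and the inserted implants in millimeters". Apical global deviation (AGD) is "the distance between the apical endpoints of the planned and the inserted implants in millimeters".
- Vertical linear deviation (VLD) begins "vertical linear deviation ; the distance between perpendicular line on the hexagon of planned implant". Apical vertical deviation (AVD) begins "apical vertical deviation ; the distance between perpendicular line on the apex of planned implant".

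The same section states that "secondary outcomes are described by the following eight measurements", and the legend of Figure 4 follows. The Materials and methods part of the abstract says "Post-op. CBCT was used for nine measurements representing the deviations in angles, implant shoulders and apexes". No other section defines LLD or ALD.

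**The concern.** Two declared secondary outcomes share one definition. Taken at face value, the plan would report the same number twice under two names.

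The missing level also matters geometrically. If the placed implant is tilted against the plan, a line parallel to the planned axis cannot run along the placed axis; it can only cross it at one point. The distance then depends on which point is chosen. Tilt is to be expected, because angular deviation is the primary outcome.

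A second reader with only the two definition clauses could not reproduce either measurement. If two readers chose different heights, values of LLD or ALD would not be comparable between cases.

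**Working it through.** **1. Compare the definitions.** With the labels removed, the LLD and ALD clauses match exactly, and neither contains hexagon, apex, apical, coronal or crest. The VLD and AVD clauses differ in a single term: putting apex in place of hexagon in VLD gives AVD exactly. The lateral pair is therefore the only one in which the change of level was not carried through. That is what a copying slip looks like.

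**2. Count the outcomes.** The secondary outcomes named are CGD, AGD, VLD, LLD, AVD, ALD, the distance to the nerve and the distance to the sinus: 6 + 2 = 8, as the section states. Adding angular deviation gives 8 + 1 = 9, as the abstract states. Merging LLD and ALD would give 7 and 8, and both stated counts would fail. The plan intends two different quantities.

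**3. Find the level elsewhere in the plan.**

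| Source | What it implies |
|---|---|
| Label of ALD | Apex |
| Abstract, Materials and methods | Measurements cover the angle, the shoulder and the apex |
| Figure 4 legend, (a) to (c) | LLD is listed with VLD and the crestal global deviation |
| Figure 4 legend, (d) to (f) | ALD is listed with AVD and AGD |

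The order of the legend helps most with LLD, whose name carries no level. It is listed with the two measures taken at the coronal end, and ALD with the two taken at the apex. The drawing itself is not reproduced in the text available for review, so it cannot be treated as silent on the level.

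**4. Size, for scale only.** Two points a distance L apart on a straight implant, tilted by angle t to the planned axis, differ in lateral offset from that axis by at most

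L × sin(t).

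The plan gives a product code but no stated length, and no expected angles. Both are assumed here: L of 8 to 12 mm and t of 1 to 10 degrees.

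| Tilt t | L = 8 mm | L = 10 mm | L = 12 mm |
|---|---|---|---|
| 1° | 0.14 mm | 0.17 mm | 0.21 mm |
| 2° | 0.28 mm | 0.35 mm | 0.42 mm |
| 5° | 0.70 mm | 0.87 mm | 1.05 mm |
| 10° | 1.39 mm | 1.74 mm | 2.08 mm |

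For example, 10 × sin(5°) = 10 × 0.0872 = 0.87 mm. These are upper limits. The lower limit is zero, since the crest and the apex can be equally far from the planned axis on opposite sides. The table shows how far LLD and ALD can differ when both are read correctly. It does not estimate measurement error in the trial.

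**5. What could change in the results.** Angular deviation, the two global deviations, the two vertical deviations and the two anatomical distances do not use the lateral definitions. Only LLD and ALD could be touched, and only if someone read them at a level other than the one their names and the legend indicate. If both had been read at one common level, the two columns would agree for every implant, and that would show on a first look at the data.

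**The case for a change.** The strongest case for acting is that a written definition should stand without its label or a figure. AVD and AGD also carry apical in their names, yet their definitions still state the apex. LLD has no level in its name, and the abstract does not assign one to it. The legend gives names, not landmarks. The repair would be a few words.

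Much of this stands. The two definitions are incomplete, and the crestal level for LLD is inferred rather than stated. But incomplete is not wrong. Each clause follows a label that is part of the definition, and the legend places LLD with the crestal measures. The Figure 4 drawing may well mark both landmarks.

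A fuller rewrite also has a cost. Recasting the outcomes as perpendicular distances from the planned axis to a point would replace the plan's construction of parallel lines. If those lines were drawn in one cross-sectional view, which the text does not settle, a three-dimensional distance would be a different quantity. Such a rewrite could also merge the hexagon with the centre of the coronal end, which the plan uses as separate landmarks. It could bring in a discrepancy where there is now only a missing word.

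**Conclusion.** No change to the plan is needed. The LLD and ALD definitions are identical in wording and omit the level, most probably through a copying slip in one sentence. The intended reading, LLD at the crest and ALD at the apex, follows from the outcome names, the abstract, the counts of eight and nine, and the order of the Figure 4 legend. A competent measurer would fill the gap that way.

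The slip concerns the wording of two of the eight secondary outcomes and does not touch the primary outcome. Nothing in the documents indicates that an implant was measured at the wrong level, and no effect on the comparison of the two techniques has been shown. The millimetre figures rest on assumed lengths and angles and have a floor of zero.

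The conclusion assumes that the Figure 4 drawing agrees with its legend. If the drawing put LLD somewhere other than the crest, the point would need to be looked at again.
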